#### **Study Duration:**

Part 1 is projected to last 30 to 72 weeks. It is projected that approximately one subject will be accrued every two weeks. Part 2 is projected to last an additional 72-104 weeks Subjects, as long as they are available for follow-up, will be followed monthly for 12 months following last dose administration for survival and quarterly thereafter.

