# 7. STUDY OBJECTIVES

#### 7.1. PRIMARY OBJECTIVES

- 1. To determine the safety of AlloStim® combined with cryoablation vs AlloStim® alone.
- 2. Determine the schedule that provides the greatest efficacy and least adverse events

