# **Toxicity Monitoring**

Two types of toxicity are assessed for determination of whether a Dose Limiting Toxicity (DLT) has occurred. An acute dose limiting toxicity (ADLT) is assessed within 48h of a dose administration during the priming, vaccination and activation steps of each protocol. Cumulative dose limiting toxicity (CDLT) is assessed during the complete Safety Evaluation Period including any ADLT that occurs in the booster dosing.

An ADLT is defined as the occurrence of any of the following within 48h of dosing:

- Any  $\geq$  Grade 3 local injection site reaction;
- Any  $\geq$  Grade 3 graft vs host disease;
- Any  $\geq$  Grade 3 infusion related symptoms of duration > 2 days;
- Any  $\geq$  Grade 4 infusion reaction of any duration

For any Grade 1-2 acute toxicity, the study drug administration schedule can continue to the next scheduled dose. If an ADLT is observed, the subject will be followed until the toxicity is resolved or the subject is stable. No further dosing for that subject will occur after an ADLT event

A CDLT event is defined as the occurrence of any of the following within the Safety Evaluation Period

- Any  $\geq$  Grade 3 graft vs. host disease
- Any toxicity  $\geq$  Grade 3 that is probably or definitely related to the study drug;
- Any toxicity not present at baseline that occurs at  $\geq$  Grade 4
- Any autoimmune toxicity  $\geq$  Grade 3 not present at baseline

All adverse events (AEs) and serious adverse events (SAEs), regardless of attribution to the study drug, will be coded, graded and become part of the final safety report for each cohort. The DSMB will review the safety data on each cohort and recommend whether to advance enrollment to the next cohort.

The development of any Grade 4 or greater toxicity in any subject at any time will prompt a review of safety data by the Sponsor, PI and the DSMB prior to accrual of any additional subjects. It is recognized that Grade 4 events and death can occur in this population due to disease progression. Therefore, dosing will continue for currently enrolled subjects at the occurrence of a grade 4 event according to protocol unless the PI determines the event is definitely or probably related to the study drug. If attribution is assigned to the study drug dosing will be suspended pending review by DSMB.

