In accordance with the 3+3 design, three subjects will be accrued into the first dosing schedule. If during the priming, vaccination and activation steps no ADLT are observed in any of the three subjects, accrual into the next cohort is allowed. If an ADLT occurs in two of the three subjects, no further dosing is allowed. If ADLT occurs in one of the three subjects, three additional subjects will be accrued into the same cohort. If no ADLT occurs within the additional three subjects, accrual into the next cohort can begin. If an ADLT is observed in any of the additional three subjects, no further dose escalation is permitted.

The development of any DLT toxicity in  $\geq$  33% of the accumulated number of subjects in any and all dosing schedules during the Safety Evaluation Period will result in protocol discontinuation.

At the completion of the Safety Evaluation Period for all cohorts, the safety evaluation of Part 1 will be considered completed and all enrollment will be closed. Efficacy evaluation will continue monthly for each subject until death or loss to follow-up.

# Part 2

The safety and efficacy data from Part 1 will be evaluated and the favored schedule advanced to Part 2. In Part 2 of the trial, up to 25 additional subjects may be accrued.

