#### **15.7.** STOPPING RULES

An external DSMB will oversee this study. The investigators and representatives of the Sponsor and DSMB will review and discuss subject data for all subjects enrolled by teleconference. The DSMB could recommend stopping the clinical trial for safety purposes.

The development of dose limiting toxicity (DLT) in any subject will prompt a review of safety data by DSMB. The development of any DLT toxicity in  $\geq 33\%$  of the accumulated number of subjects at any dosing during the assessment period (28 days after last booster infusion) will result in protocol discontinuation. However, if DTLs only occur in the Activation or Booster phase, then a decision by DSMB may be made to continue enrolling subjects to receive only priming and in-situ vaccination phases.

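### The 3+3 and the 33% stopping rule can order opposite actions at one ADLT in three, and on a pooled count nothing keeps A-2 out of Part 2 at two in six

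*Combined protocol and SAP*

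**What the plan says.** Part 1 enters three subjects in schedule A-1 and then three in A-2. Up to 25 more then receive the preferred schedule in Part 2 (Section 8).

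- **3+3 rule.** Section 8, Toxicity Monitoring, and the matching text in Section 3 say: "If ADLT occurs in one of the three subjects, three additional subjects will be accrued into the same cohort". If a further ADLT follows in the expanded cohort: "If an ADLT is observed in any of the additional three subjects, no further dose escalation is permitted". At two of three, Section 3 bars only further escalation of dose frequency, while Section 8 bars further dosing.
- **33% rule.** Section 8 (and Section 3) says a DLT in at least "33% of the accumulated number of subjects in any and all dosing schedules during the Safety Evaluation Period will result in protocol discontinuation". Section 15.7 applies the same limit to a count worded differently: "of the accumulated number of subjects at any dosing during the assessment period (28 days after last booster infusion) will result in protocol discontinuation". Section 15.7 adds that if DLTs are confined to the Activation or Booster phase, the DSMB may let enrolment continue with priming and vaccination only.
- **What counts as a DLT.** Section 8: "Two types of toxicity are assessed for determination of whether a Dose Limiting Toxicity (DLT) has occurred". The two types are ADLTs and cumulative DLTs (CDLTs), so every ADLT enters the 33% count. A CDLT includes any new toxicity of Grade 4 or above, whatever its cause.
- **Other protections.** A subject with an ADLT gets no further doses. A DLT in any subject prompts DSMB review (Section 15.7). Grade 4 or greater toxicity "will prompt a review of safety data by the Sponsor, PI and the DSMB prior to accrual of any additional subjects".
- **Choice for Part 2.** It rests on Part 1 safety and efficacy data and on the objective in Section 7.1: "Determine the schedule that provides the greatest efficacy and least adverse events". No ADLT limit is given.

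**The concern.** Both rules are written as mandatory, and neither refers to the other. One ADLT among the first three A-1 subjects is the most ordinary trigger of a 3+3, and it also reaches 33% of the subjects accumulated so far. The word accumulated suggests a running count, but no section says when the check is made, from how many subjects, or which rule wins.

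The second weakness lies at the end of Part 1. A ban on further escalation protects later cohorts. After A-2 there is no later cohort, only Part 2, so a schedule that has failed the 3+3 could still be the one expanded.

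Safety is the primary endpoint. The action at each toxicity count should be fixed before the counts are known.

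**Working it through.** Section 16.1.8 sets at least three subjects per schedule by judgement. It gives no target DLT rate and no operating characteristics, so there is no planned figure to reproduce.

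**1. The result at one in three.** 1/3 = 33.3%, which is at least 33%. A running count would also trip at 1/1 or 1/2. If the check waits until A-1 has six subjects, 1/6 = 16.7% and there is no conflict.

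**2. Two in six in A-2, counting ADLTs only.**
- Pooled after 0/3 in A-1: 2/9 = 22.2% (highest running value 28.6%).
- Pooled after 1/6 in A-1: 3/12 = 25.0% (highest running value 30.0%).
- Per schedule: 2/6 = 33.3%, which meets the limit.
- Pooled, 2 of 3 in A-2 does stop the trial (2/6 or 3/9 = 33.3%), and so does 3 of 6 (3/9 or 4/12 = 33.3%). So 2 of 6 is the only A-2 result that fails the 3+3 without a stop.

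**3. The four readings the text allows.**

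| Denominator | Checked | One of three | Two of six in A-2 |
|---|---|---|---|
| Pooled | As subjects accumulate | Conflict in A-1 | No stop |
| Pooled | End of Safety Evaluation Period | No conflict | No stop |
| Per schedule | As subjects accumulate | Conflict in either schedule | Stop |
| Per schedule | End of Safety Evaluation Period | No conflict | Stop |

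**4. Choice of ADLT rate p (assumed).** The documents give none. As a proxy, 0 of 42 subjects in the earlier ITL-002-CRYO study had a Grade 3 or higher allergy/immunology or flu-like event (Section 6.6.1). The one-sided 95% upper bound is 1 − 0.05^(1/42) = 0.069.

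**5. Chance of exactly one ADLT in the first three.** q = 3p(1−p)².
- p = 0.05: 3 × 0.05 × 0.9025 = 0.135
- p = 0.069: 3 × 0.069 × 0.8668 = 0.179
- p = 0.10: 3 × 0.10 × 0.81 = 0.243

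**6. Chance of the pooled A-2 gap at p = 0.069.**
- Running check (A-1 must be 0/3): (1−p)³q² = 0.8070 × 0.0322 = 0.0260.
- End-only check (A-1 at 0/3 or 1/6): 0.0260 × (1 + 0.1794) = 0.0306.
- One CDLT in any other subject would bring the count to 3/9 or 4/12 and close the gap. Five Grade 4 entries in Section 6.6.1 correspond to 2 to 5 of 42 subjects. Take c = 2/42 or 5/42, assumed independent of ADLTs.
- Running: 0.0260 × (1−c)⁷ = 0.0185 or 0.0107.
- End-only: 0.0260 × [(1−c)⁷ + q(1−c)⁹] = 0.0215 or 0.0122.

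The gap is therefore about 1% to 3%.

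**7. Cost of an end-only check.** The A-1 3+3 decision uses ADLTs through the day 28 dose. The Safety Evaluation Period ends 28 days after the last dose: day 56 with no booster, day 112 with both. The lag is 56 − 28 = 28 to 112 − 28 = 84 days. Section 3, Study Duration, says: "It is projected that approximately one subject will be accrued every two weeks". That is 28/14 = 2 to 84/14 = 6 further subjects.

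**The case against.** The best defence is that the conflict depends on an awkward reading. A check from the first subject would end the protocol at 1/1, so the 3+3 expansion could never operate. It would also stop the trial for a single disease-related Grade 4 event among the first three, although Section 8 continues dosing of enrolled subjects after such an event unless it is attributed to the drug. Both statements of the 33% rule name an assessment window, and reading the rule at the end of that window removes the conflict. This stands as a plausible account of intent. The text does not say it, though, and an end-only check would act late.

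The DSMB exception also softens the conflict. In A-1 the first intravenous dose is the activation dose, so infusion-related ADLTs counted by the A-1 3+3 would fall in the phase the exception covers. But the exception is discretionary, does not reach ADLTs in priming or vaccination, and leads to a third course (priming and vaccination only) rather than to expansion on the full schedule.

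A reader might infer that two of six in A-2 triggers no action at all. The documents do not support that. DSMB review follows any DLT, affected subjects get no further doses, and the selection objective must weigh adverse events. Leaving the choice to the DSMB is a legitimate design. What is missing is narrower: a rule that stops A-2 or makes it ineligible for Part 2.

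**Conclusion.** The concern holds in a conditional form. If the 33% rule is applied as subjects accumulate, one ADLT in three requires both expansion and discontinuation, with a chance of 13.5% at p = 0.05, 18% at 0.069 and 24% at 0.10. These are chances of exactly one ADLT in three. They ignore CDLTs and do not remove cases where the DSMB could use its exception. It would be too strong to say that the two rules always contradict each other, since an end-of-period check avoids it.

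The difference between Sections 3 and 8 at two of three needs no assumption.

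The missing Part 2 bar matters only on the pooled reading, which is the more natural one for Section 8. It is the less likely problem. Every probability here rests on an assumed ADLT rate, and the 0.069 bound also rests on the proxy used for it. This is worth settling by amendment because the change is cheap and the rules govern the primary endpoint. DSMB oversight means it is not fatal to the design.

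**What to change.** Amend Sections 3, 8 and 15.7 together.

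1. State that the 33% rule uses all subjects pooled and is applied as subjects accumulate, but only once at least six subjects have been treated or two subjects have had a DLT. Until then the 3+3 governs, so a single ADLT in three leads to expansion.
2. State that when the 33% rule is met, protocol discontinuation, subject to the DSMB exception in Section 15.7, overrides the 3+3 action. Without this, stopping one schedule at two of three would clash with stopping the protocol: 2/3 in A-1 is 67%, and 2/3 in A-2 after 0/3 is 2/6 = 33.3%.
3. At two of three, use *no further dosing on that schedule* in both Sections 3 and 8.
4. Add: *A schedule with 2 or more ADLTs in up to 6 subjects may not be selected for Part 2.*

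The cost is wording in three sections and the DSMB charter, with no added procedures. There is slightly less freedom in choosing the Part 2 schedule. Before CDLTs are counted, the bar would exclude A-2 at two of six in (1−p)³(1+q)q² of trials: 0.8574 × 1.1354 × 0.0183 = 1.8% at p = 0.05, and 0.7290 × 1.2430 × 0.0590 = 5.4% at p = 0.10.

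The 33% rule can still stop a schedule that passed the 3+3, because it counts any new Grade 4 or higher event. With c = 2/42 to 5/42, A-1 at 0/3 ADLTs would stop in 3c²(1−c) + c³ = 0.7% to 3.9% of cases, and A-1 at 1/6 in 1 − (1−c)⁵ = 22% to 47%. The sponsor should accept that knowingly.

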# 9. STUDY ENDPOINTS

# 9.1.PRIMARY ENDPOINT

Safety will be the primary endpoint of this study and will be evaluated on the basis of the following parameters:

- Physical examination and vital signs (temperature, blood pressure, pulse rate, respiratory rate, and blood oxygen saturation).
- Clinical laboratory profile (complete blood count (CBC), comprehensive metabolic panel (CMP), C-reactive protein (CRP), coagulation factors and autoimmune parameters.
- Adverse events according to the National Cancer Institute (NCI) Terminology Criteria for Adverse Events (CTCAE) version 4.03 (refer to section 15 for AE/SAE management and reporting):

# **9.2. EXPLORATORY ENDPOINT**

- Correlation of tumor burden by RECIST, pathological response and immune response to Overall Survival (OS).
  - Overall Survival (OS) is evaluated from time of enrollment until death from any cause. Subjects are followed for survival during the trial, as long as they are alive, for 12 months after the last study treatment through follow-up phone calls.
  - Traditionally, oncology investigators have relied upon Response Evaluation Criteria in Solid Tumors (RECIST) to serve as a surrogate to predict clinical benefit. RECIST criteria for clinical outcomes rely upon the assumption that agent activity results in shrinkage of tumor and that enlargement of disease is a result of tumor growth. RECIST is a composite evaluation of response based upon measurements of the changes in tumor size [82]. RECIST criteria have been criticized for not being a reliable method to predict OS benefit for cytotoxic agents [83].

In order to determine the utility of RECIST in evaluating response of patients to immunotherapy, RECIST 1.1 [82] guidelines will be used to determine objective tumor response. This endpoint will be determined and analyzed for correlation with OS. Malignant tumor masses (target lesions) will be selected on the basis of their size and their suitability for accurate repetitive measurements. All patients must have at least one target lesion that can be accurately measured in at least one dimension (longest diameter to be recorded) greater than or equal to 1.0 cm with spiral CT scan. To assess objective response, it is necessary to estimate the overall tumor burden at baseline and use this as a comparator for subsequent measurements. Whenever possible, several measurable lesions, up to a maximum of 2 lesions per organ and 5 total target lesions representative of involved organs, should be identified, measured and recorded at baseline. To allow later retrieval, lesions should be clearly marked on the films or otherwise identified. If the lesion is detected by more than one method at baseline, the investigator should select at baseline the method to be used at subsequent evaluations. All measurements should be performed using a caliper or ruler and should be recorded in metric notation in centimeters. A sum of the longest diameter for all target lesions will be calculated and reported as the baseline sum longest diameter. The baseline sum longest diameters will be used as reference to further characterize the objective tumor response of the measurable dimension of the disease by repeated assessment of the sum of the longest diameters during treatment.

All other lesions (or sites of disease) should be identified as non-target lesions and should also be recorded at baseline. Measurements are not required and these lesions should be followed as "present" or "absent". All baseline evaluations should be performed as closely as possible to the treatment start and never more than 14 days before the beginning of the treatment.

RECIST evaluations are particularly problematic for evaluating responses to immunotherapy, as the mechanism of action of immunotherapy drugs may cause swelling or flare of tumors, resulting in the appearance of increased size on CT scans, but may actually represent decreased burden of viable tumor. In addition, immune-mediate responses may manifest after an initial increase in tumor burden or may delay or stop tumor growth, resulting in disease stabilization and increased survival, but will be scored as progressive disease by RECIST criteria. Therefore, RECIST may erroneously predict progression in a subject treated with immunotherapy.

For this reason, this study proposes:

- 1. Longitudinal serial biopsies for comparison and correlation with RECIST data in order assess whether RECIST can be used to predict survival when using this immunotherapy.
- 2. Evaluation of subjects according to newly proposed immune-related response criteria (irRC) [85]. The irRC is thought to better address patients' treatment, investigators' patient management and sponsors' analysis needs for targeted immunotherapy developments in oncology.
- Subjects treated on this study will undergo evaluation of immune response to treatment. The results will be used to correlate response to vaccination with subsequent clinical outcome and OS.

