# **11. STUDY PLAN AND PROCEDURES**

# 11.1. OVERALL STUDY PLAN

Subjects will be screened for eligibility for the study. The screening process involves examining medical records to determine eligibility based on the IC/EC criteria. After obtaining informed consent, subjects will undergo physical exam, provide blood for lab analysis (CBC, CMP, total IgG and IgM, lipase, erythrocyte sedimentation rate, and CRP), an ultrasound of the liver, and a CT scan. The results of these baseline tests will be reviewed by the Principal Investigator (PI) and the Sponsor's medical monitoring team to determine if the subject still meets IC/EC. In schedule A-1, the study interventional radiologist will determine if the subject has a lesion assessable for cryoablation. If the subject meets IC/EC criteria, a biopsy and tumor harvest procedure will be conducted.

When the PI and the Sponsor agree that all IC/EC criteria are met, the subject is accrued/ enrolled in the study and assigned a protocol number. The enrollment date will be documented in CRF/eCRF. Upon accrual, the study site develops an appointment schedule for the subject and sends to the Sponsor for approval. Upon approval, the subject is notified of the schedule. The Sponsor will produce and ship AlloStim® in accordance with the approved schedule.

AlloStim® will be formulated in Israel by the Sponsor, packaged in validated temperaturecontrolled container and delivered by specialized courier service to the study site at least one day before the established treatment schedule day. AlloStim® is stable in formulation for at least 72 hours. All protocol required CT scans will be conducted at a radiology center. Cryoablation, intratumoral AlloStim® and voluntary tumor biopsies will be conducted at a radiology center.

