#### **12.2.** Screening Assessments for all Schedules

Any subjects deemed possibly eligible for participation will be recruited and assigned a screening number. Before screening assessments are conducted, the PI or designated representative will explain the protocol procedures, including timing; the expected and unknown risks and possible benefits; and answer all subject's questions and concerns. The informed consent procedure should be documented in the source record and include at least the following: (1) subject screening number; (2) date and time; (3) person performing the consent procedure; (4) persons present during the consent procedure and their relationship to the subject or the study; (5) document any questions asked or concerns expressed by subject or subject's representative(s); (6) confirmation that subject understands that participation is voluntary and can withdraw at any time without penalty, that the protocol is experimental, that no particular outcome can be assured or is known, that there is the possibility of side-effects some of which may be serious, and that the protocol requires commitment of significant time to visit clinic and participate in telephone interviews. Subsequently, the subject must sign and date and receive a copy of an informed consent document that was approved by the Institution Review Board (IRB) or Independent Ethics Committee (IEC) before any study specific procedure is performed. An additional signed copy should be retained and placed in the Study File.

Baseline assessments can be initiated up to two weeks prior to the first scheduled investigational product administration (Day -14) and must be completed at least 4 day prior to the scheduled investigational product administration (Day -4) due to formulation logistics and transits times. Results of tests or examinations performed as standard of care prior to obtaining informed consent and within 14 days prior to protocol Day 0 may be used, rather than repeating required tests. The following evaluations and procedures will be performed during screening:

- Written informed consent(s)
  - Study informed consent
- Complete medical history, including disease history (date of diagnosis, prior cancer therapy and surgery, tumor/node/metastasis staging at the time of diagnosis and study entry and pre-existing toxicities from previous therapies)
- Prior (within 30 days) and current concomitant medications

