#### **16.1.6. Exploratory Endpoints**

All data will be summarized using descriptive statistics by dosing schedule. All subjects who received any study medication will be included in the analysis.

If the subject is alive at the end of the follow-up period or is lost to follow-up, OS will be censored on the last date the subject is known to be alive.

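### Overall survival is timed from enrollment but analysed only in dosed subjects, so time zero and the analysis set do not match; the effect is modest

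*Combined protocol and SAP*

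**What the plan says.** Section 9.2 fixes the origin: "Overall Survival (OS) is evaluated from time of enrollment until death from any cause". Section 16.1.6 fixes the set: "All subjects who received any study medication will be included in the analysis". The same section gives the censoring rule for subjects alive or lost at the end of follow-up, namely that "OS will be censored on the last date the subject is known to be alive". It says nothing about a subject who was enrolled and never dosed.

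Section 11.1 places enrollment before dosing. Once the investigator and the sponsor agree on eligibility, "the subject is accrued/ enrolled in the study and assigned a protocol number". Further steps follow: "Upon accrual, the study site develops an appointment schedule for the subject and sends to the Sponsor for approval". After approval, "The Sponsor will produce and ship AlloStim" to the agreed dates. Section 12.2 lets baseline work start at Day -14 and says that it "must be completed at least 4 day prior to the scheduled investigational product administration". Section 12.3 allows the final eligibility assessment as late as Day -1.

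The safety analyses (sections 16.1 and 16.1.3) are also confined to dosed subjects, and adverse event reporting starts at the first dose (section 15.3.1). ITT appears in the analysis text only in the protocol abstract, where it helps to define the safety population. The glossary expands the abbreviation, but no section defines the set.

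**The concern.** A survival clock that starts at one event, applied to a set chosen by a later event, credits every member of the set with survival between the two. Nobody in the dosed set can have died between enrollment and Day 0. A subject who does die then is an OS event by the definition in section 9.2, but is outside the set in section 16.1.6. The size of the effect depends on scheduling and drug logistics and on who fails to reach dosing, not on treatment.

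OS is the reference against which RECIST, pathology and immune response are to be correlated. There is also no untreated control group, so a reader of the curve may look to the external medians quoted in the introduction. A mismatch that can only favour the curve is worth removing while it costs almost nothing.

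**Working it through.** The plan has no OS estimate, event count or power figure to reproduce. Section 16.1.8 justifies at least 3 subjects per schedule by judgement. The check is therefore whether the mismatch exists, and how large it could be.

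**Does it exist?** Sections 9.2 and 16.1.6 name different anchors, and sections 11.1, 12.2 and 12.3 put enrollment before first dose. No section assigns OS to all enrolled subjects, uses delayed entry, or gives a rule for undosed subjects. It exists.

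**Length of the gap g (assumption; the documents do not state it).**
- 1 day: the literal minimum, from the Day -1 limit in section 12.3.
- 4 days: from the Day -4 completion limit in section 12.2.
- 14 days: an extreme. Day -14 is the earliest start of baseline work, whereas enrollment follows examination, laboratory tests, imaging, review and biopsy (section 11.1). Section 12.1 allows up to 7 days' delay for a missed appointment, but section 9.2 does not let baseline evaluations be more than 14 days old at treatment start, so 14 is kept as the upper end.

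**OS from enrollment minus OS from first dose, same dosed subjects.** The difference is g divided by 30.44 days per month, and needs no hazard assumption if all have the same gap:
- 1/30.44 = 0.03 months
- 4/30.44 = 0.13 months
- 14/30.44 = 0.46 months

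**Bias against OS from enrollment in all enrolled subjects.**
- If every enrolled subject is dosed, the two sets are identical and the bias is zero.
- If the hazard is constant and the undosed are exactly those who die in the gap, the dosed-only median from enrollment is m + g, where m is the true median, so the bias equals the gap. With m = 5.0 months the median reads 5.03, 5.13 or 5.46 for gaps of 1, 4 and 14 days. With m = 7.1 it reads 7.13, 7.23 or 7.56.

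**Share of enrolled subjects dying in the gap, constant hazard.** P = 1 − 2^(−g/m), with g in months. The medians of 5.0 (placebo) and 7.1 months (TAS-102) come from the trials described in sections 6.2.7 and 6.2.1 (TAS-102) and serve only as scale. The expected number uses the maximum of 6 + 25 = 31 subjects (section 8).

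| Gap | P, m = 5.0 | Deaths of 31 | P, m = 7.1 | Deaths of 31 |
|---|---|---|---|---|
| 1 day | 0.5% | 0.14 | 0.3% | 0.10 |
| 4 days | 1.8% | 0.56 | 1.3% | 0.40 |
| 14 days | 6.2% | 1.91 | 4.4% | 1.36 |

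These shares are upper bounds. Subjects with ECOG 0-1 who have just passed eligibility should have a lower early hazard than a constant rate implies. The table counts deaths only; a subject who deteriorates and is never dosed is also left out of the set, and the documents give no basis for a figure.

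**The case against.** A reader might infer that OS is inflated by construction by up to half a month. The documents do not support that. The 0.03 to 0.46 months is a difference between two clocks. When everyone enrolled is dosed, the gap is real survival since enrollment and nothing is biased. The larger figure also needs enrollment on the first day on which baseline work may begin.

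A reader might also set the half month against the survival gains quoted in the introduction. The result depends on the pairing: 0.46/1.1 = 42% for the longest gap against the smallest difference (regorafenib, KRAS mutant), but 0.03/2.3 = about 1% for the shortest gap against the largest (regorafenib, KRAS wild type). The protocol plans no formal comparison with those trials, so neither ratio measures an effect on a planned result.

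Nor do pre-dose deaths disappear altogether. Section 15.2.2 requires any death during the study to be reported to the sponsor. They are missing from the analyses, not necessarily from the record.

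Finally, section 16.1.6 says that dosed subjects are included and does not add that others are excluded; OS is exploratory with descriptive analysis only; and a roughly constant offset of days would hardly change a correlation with OS. These limits on consequence stand. The wording point is weaker, because no other set is named for OS. Section 11.2.4 does call OS the primary endpoint, against section 9.1, but that is a separate contradiction and this point does not rest on it.

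**Conclusion.** The mismatch is real and nothing elsewhere in the document resolves it. Each analysed subject carries pre-dose survival guaranteed by selection, and a pre-dose death enters neither the OS nor the safety analysis.

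The effect is modest. On an assumed gap of 1 to 14 days, OS from enrollment exceeds OS from first dose by 0.03 to 0.46 months in dosed subjects. Against all enrolled subjects the bias is zero if all are dosed, and equals the gap only under a constant hazard with all pre-dose deaths excluded. On that assumption, with medians of 5.0 to 7.1 months, about 0.3% to 6% of enrolled subjects die before dosing, which is an upper bound. The actual gap, and the number of enrolled subjects who go undosed, cannot be read from the documents. Because OS is exploratory and untested, this is a minor point, worth correcting because the correction is so small.

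**What to change.** In sections 9.2 and 16.1.6, match time zero to the analysis set:
- Report OS from enrollment in all enrolled subjects, stated in those words and not as ITT, since the plan does not define that set.
- Report OS from the first AlloStim dose (Day 0) in dosed subjects.
- List enrolled but undosed subjects with the reason and their outcome.

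Both OS lines are needed. Starting the clock at first dose removes the guaranteed time but still omits pre-dose deaths; only the all-enrolled line brings those back.

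The cost is about one sentence in each section, one extra line of analysis and a short listing. The enrollment date (section 11.1) and the drug administration details (Table 10, section 17.10.1) are already collected on the case report form. No visit, dose or sample size changes. The downside is that the OS estimate may become slightly shorter.
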